6. GENERAL ANALYSIS DEFINITIONS

6.1 TREATMENTS

For reporting purposes, all randomised patients will be classified into one of the following treatment groups:

Sort order	Treatment	Long label	Short label
01	B	BI 655064 120mg	BI 120mg
02	C	BI 655064 180mg	BI 180mg
03	D	BI 655064 240mg	BI 240mg
04	A	Placebo	Placebo

These will be the default labels and sort order for reporting the treatment groups.

The following study periods based on actual start and stop dates of study treatment administration are defined:

Screening: day of informed consent to day prior to the start of randomised medication

Treatment: start date of randomised double-blind medication to date of last dose

Follow-up: day after the last dose of randomised double-blind medication through trial completion and after trial completion

Rules for assigning AEs/laboratory data to the study periods are as follows.

AEs/laboratory data will be assigned to the treatment period if they occur/samples were taken after the first injection of study medication to the date of last administration of study medication plus 50 days.

Since AE onset time was not recorded, investigators were asked to provide more information for AEs with date of onset equal to date of first injection. Additional information was to be provided in the AE comment field. The trial team will review the comments & will impute a time to capture onset as prior to or following first injection of study medication. An analysis data set will be created to incorporate this information. If the site indicates that the AE onset time is prior to trial medication administration then the AE will be assigned to the screening period. If the site indicates that the AE onset time is after trial medication administration or there is no information regarding onset then the AE will be assigned to the treatment period.

Adverse events with onset on or after the 51st day after the last administration of trial medication will be considered 'Follow-up' events. However, if the patient rolls over to the extension trial (1293.13) & receives the first dose of trial medication in 1293.13, any new events or worsening of existing events will be assigned to the treatment period of 1293.13.

Laboratory data on or after the 51st day after the last administration of trial medication will be considered 'Follow-up' data.

Proprietary confidential information © 2020 Boehringer Ingelheim International GmbH or one or more of its affiliated companies

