Visits 7-8 (from week 8): syringes for the visit injection plus next 3 weeks (home) injections

Visit 9-10 (from week 16): syringes for the visit injection plus next 4 weeks (home) injections

Visit 11 (week 26): syringes for the visit injection plus next 3 weeks (home) injections

Visit 12-13 (from week 30): syringes for the visit injection plus next 4 weeks (home) injections

Visit 14-15 (from week 40): syringes for the visit injection plus next 5 weeks (home) injections

An additional syringe could be requested to accommodate for the time window when needed.

The different dose groups of BI 655064 will be double-blinded. Therefore, the patients will receive injections of BI 655064 and/or placebo to BI 655064.

Table 4.1.4: 1 Dose groups

Dose group	BI 655064 (Dose group 1)	BI 655064 (Dose group 2)	BI 655064 (Dose group 3)	Placebo (Placebo)
Dose received	120 mg weekly week 0-1-2 120 mg every two weeks week 3 to 51	180 mg weekly week 0-1-2 180 mg every two weeks week 3 to 51	240 mg weekly week 0-1-2 120 mg weekly week 3 to 51	
Syringes to be administered weekly Week 0-1- 2	120 mg BI 655064 + placebo	180 mg BI 655064 + placebo	120 mg BI 655064 + 120 mg BI 655064	Placebo to BI 655064 + Placebo to BI 655064
Syringes to be administered weekly Week 3 to 51	120 mg BI 655064 or/alternating placebo	180 mg BI 655064 or/alternating placebo	120 mg BI 655064	Placebo to BI 655064
No. of patients	20	20	40	40

No dose modification for BI 655064/placebo is permitted.

Please note that dilution of the study medication or the use of other syringes or needles than those specifically provided by the sponsor is not allowed.

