6.2.3 Follow Up Period and Trial Completion

6.2.3.1 End of Treatment (EOT) Visit:

All patients will be asked to return for the EOT visit within 7 days from the last dose of study medication (either at week 52 for completers, or when a patient prematurely discontinues the drug). For details description of the trial procedures at EOT, refer to the [Flow Chart](#). 2 times 24h collection of urine has to be organized for this visit.

For patients that are eligible to participate in the extension trial 1293.13, the EOT visit will occur on the same day as the Visit 1 of the roll-over trial.

6.2.3.2 Follow-Up (FU) and End of Study (EOS) Visit:

After the end of treatment visit, patients who completed the 52 weeks treatment but are not eligible for the extension trial will return for a follow-up visit (after 4 weeks) and an EOS visit, 8 weeks after EOT.

Patients who are eligible for the extension trial will not have to complete the FU visit nor the EOS visit, but only the trial completion page will have to be completed.

During FU and EOS visits, the investigator will continue to follow-up on AEs that are not yet recovered. At EOS visit, the investigator needs to confirm whether the AEs are sufficiently followed up and provide documentation in the patient's medical records and on the eCRF.

For details description of the trial procedures at FU and EOS visits, refer to the [Flow Chart](#).

6.2.3.3 Continuation of the study for patients who withdrew drug prematurely (before completion of the 52 weeks treatment):

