7.8.2 Laboratory data

The analyses of laboratory data will be descriptive in nature and will be based on BI standards [\(9\)](#).

The residual effect period of 50 days will be applied to the laboratory data. Laboratory data will be assigned to the treatment period if samples were taken after the first injection of study medication to the date of last administration of study medication plus 50 days. Laboratory data from samples taken on or after the 51st day after the last administration of trial medication will be considered 'Follow-up' data.

Tables and figures in Section 15 of the CTR will include laboratory data from the treatment period; data from the follow-up period will not be included. Listings of laboratory data will display on-treatment and follow-up data, with follow-up data flagged to identify they are from samples taken during the follow-up period.

Possible clinically significant abnormalities (PCSA) were identified using BI standard rules plus RCTC.

Figures displaying mean and median WBC and neutrophils over time will be provided.

Descriptive statistics for anti-double stranded DexoxyriboNucleic Acid (anti-dsDNA), Complement Component C3 (C3) and Complement Component C4 (C4) counts over time will be displayed for all patients in the treated set. For anti-dsDNA, descriptive statistics for patients who are positive at baseline [i.e., >ULN (=75 IU/mL)] will tabulated and displayed in a figure. For C3 and C4, patients who are below lower limit of normal (LLN) at baseline will tabulated and displayed in figures. LLN for C3 is 0.9 g/L. LLN for C4 is 0.1 g/L.

Descriptive statistics over time for erythro sedimentation rate will be provided.

IgG & IgM values will be listed by treatment, patient and visit. Values outside the normal range will be flagged. Possibly clinically significant abnormalities will be flagged.

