7.8.4 ECG

Descriptive statistics for mean heart rate, PR interval, QRS interval, QT interval, QTcB and QTcF absolute values and changes from baseline over time will be provided. Frequencies of subjects with notable findings in mean heart rate, PR interval, QRS interval, QT interval, QTcB at any time on treatment will be tabulated.

Notable findings for each parameter are defined as:

- HR: Increase from baseline in HR $\geq 25\%$, when the corresponding on treatment HR is > 100 bpm or decrease from baseline in HR $\geq 25\%$, when the corresponding on treatment HR is < 50 bpm.
- PR: Increase from baseline in PR $\geq 25\%$, when the corresponding on treatment PR is > 200 ms.
- QRS: Increase from baseline in QRS $\geq 10\%$, when the corresponding on treatment QRS is > 110 ms.
- New onset of QTcF > 500 ms, or increase from baseline in QTcF > 60 ms.
- New onset of QT > 500 ms.

(New onset means ‘not present at baseline’.)

Patients with notable findings for any of these parameters will have all ECG parameters displayed in one listing with flags indicating the notable findings.

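### Read literally, SAP 6.1 puts the completers' week-52/EOT ECG in Follow-up, which leaves it out of the notable-ECG table in SAP 7.8.4

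*SAP*

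**What the plan says.** SAP 6.1 builds the study periods from the actual dates of dosing. The active period is "Treatment: start date of randomised double-blind medication to date of last dose", and the next is "Follow-up: day after the last dose of randomised double-blind medication through trial completion and after trial completion". A separate block, opened by "Rules for assigning AEs/laboratory data to the study periods are as follows", then widens the period for two kinds of data. The rule begins "AEs/laboratory data will be assigned to the treatment period if they occur/samples were taken after the first injection of study medication to the date of", and its end point is 50 days after the final injection. SAP 7.8.1 repeats the 50 days for adverse events. SAP 7.8.2 does the same for laboratory values: "The residual effect period of 50 days will be applied to the laboratory data". No sentence gives ECG the same extension.

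SAP 7.8.4 plans two ECG summaries. Values and changes from baseline are described over time, with no on-treatment limit. The count of patients with notable findings is limited; its sentence ends "QTcB at any time on treatment will be tabulated". The heart rate, PR and QRS criteria also require the post-baseline value to be an on-treatment one. A patient with a notable finding then has all ECG parameters shown in one flagged listing.

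Two other places bear on the point. SAP 6.7 says that visits with 'Visit' or 'FU' in the label came after EOT and were off drug; the labels for the EOT visit itself contain neither word. Protocol 7.3.4 says that other safety-relevant data, including those from the end-of-trial evaluation, will be assessed for change from before treatment.

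**The concern.** For a completer, the EOT ECG is the only scheduled one after week 40. For an early stopper it is the one nearest the stop. The Protocol's abbreviation list describes the residual effect period as the time after the last dose when drug levels or pharmacodynamic effects are likely to remain. That is a statement about exposure and does not depend on the kind of measurement. Yet under 6.1 a blood sample and an ECG from the same EOT visit would go to different periods.

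At stake is the by-arm count of notable ECG findings. With 20 or 40 patients per arm, one uncounted patient changes an arm's rate by 1/20 = 5 or 1/40 = 2.5 percentage points. Two programmers, one following 6.1 and one following 6.7, could also produce different tables from the same data.

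**Working it through.** **Inputs**
- ECG visits (Protocol flow chart): baseline, then weeks 4, 12, 26, 40 and 52/EOT, so 5 after baseline. There is none at visits 17 and 18.
- Last dose for completers: Table 4.1.4: 1 runs dosing to week 51. The dispensing schedule agrees: "Visit 14-15 (from week 40): syringes for the visit injection plus next 5 weeks (home) injections", so visit 15 at week 46 covers weeks 46 to 46 + 5 = 51. The flow chart shows no administration at visit 16.
- Windows: home injection ±1 day (Protocol 4.1.4); visit 16 on day 365 ±3 (flow chart).
- EOT visit: "All patients will be asked to return for the EOT visit within 7 days from the last dose of study medication" (Protocol 6.2.3.1).

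**Calendar check.** Day = 7 × week + 1 reproduces the flow chart: week 4 = 29, week 12 = 85, week 26 = 183, week 40 = 281, week 46 = 323, week 52 = 365.

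**Completers**
- Last dose: 7 × 51 + 1 = day 358.
- Nominal gap to EOT: 365 − 358 = 7 days.
- Shortest gap: (365 − 3) − (358 + 1) = 3 days.
- Longest gap: (365 + 3) − (358 − 1) = 11 days. The 7-day request in 6.2.3.1 would cap this lower, but the shortest gap is unaffected.
- Protocol 4.1.4 allows an extra syringe to bridge the visit window. If it were used on about day 365 (±1) with EOT on day 368, the gap would still be 368 − 366 = 2 to 368 − 364 = 4 days.

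The 6.1 treatment period ends at gap 0, so a completer's EOT ECG lies outside it. That is 1 of 5 scheduled post-baseline ECGs (20%). The last one counted is at day 281, which leaves (358 − 281)/7 = 11 weeks of dosing with no scheduled ECG in the table.

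**Early stoppers.** The gap is 0 to 7 days. At 0 the ECG is on treatment; at 1 to 7 it is in Follow-up. A patient who stops before week 4 and has EOT at least one day after the last dose would have no scheduled post-baseline ECG in the table.

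**With a 50-day extension for ECG.** The longest gaps are 11 days (completers) and 7 days (early stoppers), both under 50. All 5 scheduled post-baseline ECGs then count for completers, against 4 of 5.

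**The case against.** The strongest reply is that the exclusion is inferred. SAP 7.8.4 does not cite the 6.1 period, and 6.7 implies that EOT is not an off-drug visit. Protocol 7.3.4 wants end-of-trial data assessed, and SAP section 4 announces no departure from that. SAP 7.8 also defers to company standards that are not in the documents and might set an ECG window. This stands to the extent that the loss follows from a literal reading and is not certain. It does not remove the point: 6.1 holds the only period definition in the SAP that could apply to ECG, and 6.7 is a note on visit labels. A conflict between the two is itself a reason to settle the text.

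The reply on harm stands too. EOT ECGs remain in the over-time summaries and in the individual listings planned in SAP 7.8. Protocol 5.3.4 requires clinically relevant ECG findings to be entered as adverse events, which do get the 50 days, and adverse events leading to discontinuation have their own table. A reader might infer that a patient who stops for a cardiac reason disappears from the by-arm safety counts; the documents do not support that. What can be lost is a threshold-only change not judged clinically relevant.

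A reader might also infer that every patient's EOT ECG is lost. That is too broad. Protocol 6.2.3.1 allows EOT on the day of last dose, and Protocol 6.2.2 has it completed at whichever visit the decision to stop is made.

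Nor is a matching defect shown for vital signs: SAP 7.8.3 plans descriptive statistics with no on-treatment limit.

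**Conclusion.** The point holds on the text, with limited reach. Followed as written, SAP 6.1 and 7.8.4 leave out the week-52/EOT ECG of every completer seen in window, and the EOT ECG of any early stopper assessed after the day of last dose. The effect is confined to the notable-findings table and its flagged listing, in a descriptive safety analysis with no hypothesis testing.

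This rests on three assumptions: that on treatment in 7.8.4 means the 6.1 treatment period; that the completer's last injection is the scheduled week-51 one, or an extra one given before the day of the EOT visit; and that no company standard outside the documents sets a different ECG window. The documents do not say how many early stoppers would have EOT after the day of last dose, so no count is given for them.

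**What to change.** State in SAP 6.1 or 7.8.4 that ECGs up to last administration plus 50 days count as on treatment for the notable-findings table, and say that this includes the EOT ECG. Align 6.1 with the visit-label note in 6.7, so that both treat EOT alike. Leave 7.8.3 as it is.

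The cost is one sentence and one derivation line, with no new data. The change should bring in little else: the follow-up visits have no scheduled ECG, and Protocol 6.2.3.3 does not list ECG among the examinations after early discontinuation. Beyond the EOT record, only unscheduled control ECGs within the 50 days would be added.

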6.2 IMPORTANT PROTOCOL DEVIATIONS

The following table defines the different categories of important protocol deviations (iPDs). The final column indicates which iPDs will be used to exclude patients from the different patient analysis sets.

Patients with iPDs will be documented. The following list of iPDs will be used; note that this is a working list and may not be finalised until the final Report Planning Meeting (RPM) prior to database lock.

Excluded from ‘None’ denotes a safety iPD.

Table 6.2: 1 Handling of iPDs

Category/ Code	Description	Example/Comment	Excluded from
A	Entrance criteria not met		
A1.1	Inclusion criteria 3, 4 or 5 not met	Inclusion criteria, 3, 4 (including biopsy class, active or active/chronic disease and time between biopsy & screening) or 5 not met as specified in the protocol (automatic PD)	PPS
A1.2	Inclusion criteria 1 not met	Inclusion criteria 1 not met as specified in the protocol (automatic PD)	None
A2	Exclusion criteria 2, 3, 4, 7, 10-12 met*	Exclusion criteria 2, 3 [4], 4 [5], 7 [8B], 10 [11], 11 [12A or 12B], 12 [13] met as specified in the protocol (automatic PD)	PPS/ (TBD at MQRM/ BRPM)
B	Informed consent		
B1	Informed consent not available/not done	Informed consent date missing (automatic PD)	All
B2	Informed consent too late	Informed consent date <actual consent date> was after Visit 1 date <Visit 1 date> (automatic PD)	None
C	Trial medication and randomization		
C1	Randomization not followed	Patient not treated according to randomization.	PPS/ (TBD at MQRM/ BRPM)
C2	Wrong dosage schedule	Wrong dose of BI 665064 taken or syringes used in the wrong order	PPS/ (TBD at MQRM/ BRPM)
C3	Non-compliance with study medication	Any evidence of gross non-compliance (manual or automatic PD) as defined in Section 5.4 . iPDs were not assigned if a patient had documented reasons for non-compliance such as AE (which was allowed per protocol) or drug not at site.	PPS/ (TBD at MQRM/ BRPM)

Proprietary confidential information © 2020 Boehringer Ingelheim International GmbH or one or more of its affiliated companies

Table 6.2: 1 (continued) Handling of iPDs

Category/ Code	Description	Example/Comment	Excluded from
C4	Medication code broken inappropriately	Medication code broken inappropriately - reason for medication code break <reason> (manual PD)	PPS
D	Concomitant medication		
D1	Prohibited medication use	
 • Azathioprine during weeks 0-26 • Cyclophosphamide 6 months prior to randomization through Week 52 • Cyclosporine-Tacrolimus during 4 weeks prior to randomization through Week 52 • Any biologic B-cell depleting therapy (e.g. anti-CD20, anti-CD22) or Abatacept during 12 months prior to randomization through Week 52 • anti-Blyss 3 months prior to randomization for non renal SLE or 12 months for renal SLE through Week 52 • Investigational medication for 6 months or 5 half lives prior to randomization through week 52 • IV glucocorticoids during Week 40-52. (Manual iPDs)	PPS/ (TBD at MQRM/ BRPM)
D2	Non-permitted oral steroid use	Patient used more than 10 mg per day of oral steroid at any time during the interval from week 40 to week 52.	PPS/ (TBD at MQRM/ BRPM)
D3	Non-permitted MMF dose	MMF >3g per day up to week 26 or average MMF >2.5 g per day after week 26	PPS/ (TBD at MQRM/ BRPM)
G	Trial specific		
G1	Failure to remove patient from therapy	As described in CTP section 3.3.4.	PPS/ (TBD at MQRM/ BRPM)
Z	Other		
Z1	Other iPDs affecting efficacy and possibly safety		PPS/ (TBD at MQRM/ BRPM)
Z2	Other iPDs affecting safety only		None

*The numbering of exclusion criteria changed with one or more of the protocol amendments. The numbering, reflected in the data sets and in later eCRFs, is shown in brackets.

Proprietary confidential information © 2020 Boehringer Ingelheim International GmbH or one or more of its affiliated companies

6.3 SUBJECT SETS ANALYSED

- **Randomised set:**
This patient set includes all randomised patients, whether treated or not.
- **Treated set:**
This patient set includes all patients who were dispensed study medication and were documented to have taken at least one dose of investigational treatment.
- **Intent to treat (ITT) set:**
This patient set includes all patients from the treated set who have a baseline (or screening) proteinuria (spot urine can be used if patient does not have 24-hour collections) and baseline or screening eGFR
- **Per protocol set (PPS):**
This patient set includes all patients in the ITT who completed at least 46 weeks of the treatment regimen and do not have iPDs leading to exclusion from the PPS as defined in [Table 6.2: 1](#)

Table 6.3: 1 Subject sets analysed

Class of endpoint	Patient set		
	Treated set	ITT	PPS
Primary endpoint: CRR at week 52		X (primary analysis)	X
Secondary endpoints		X	X
Safety endpoints	X		
Demographic/baseline endpoints	X		

Note that the number of patients with available data may differ across endpoints. For details, see [Section 6.6](#) “Handling of missing data”.

6.5 POOLING OF CENTRES

Centre is not a term in the model. Therefore, no pooling of centres needs to be performed.

6.6 HANDLING OF MISSING DATA AND OUTLIERS

6.6.1 Primary and secondary endpoints

As CRR is defined based on UP (and UP/UC) from the two 24h urine collections and eGFR calculated from serum creatinine, rules for derivation of CRR when one or both of the urine samples and/or the serum sample is missing are specified below.

If one 24h urine collection is missing at any time point, then calculations should be based on the available 24h collection at that time point. If one 24h urine collection at any time point is suspected to be incomplete (<500mL/day or time of collection is <19.5 hours) or otherwise not evaluable, then calculations should be based on the unaffected collection at that time point.

Note that the restrictions on volume and duration of collection do not apply to the UP/UC derivation as the adjustment using UC is thought to compensate for incomplete collections.

If both 24h urine collections at baseline are missing, suspected to be incomplete or not evaluable, then UP/UC from the spot urine at baseline should be used to impute baseline UP (or UP/UC) from a 24h collection.

Handling missing data for patients who do not prematurely stop trial medication

If a patient does not have 24h urine collections at week 26 or at week 52, then UP from a 24h collection will be imputed as follows:

- For the week 26 UP, use the mean of UP/UC from the spot urines at weeks 21 and 26
- For the week 52 UP, use the mean of UP/UC from the spot urines at weeks 46 and 52

UP/UC from two weeks are used to get a more stable estimate of UP as it is generally accepted that estimates from the spot urines are not as reliable as estimates from the 24h collections.

For the derivation of CRR using UP/UC from the 24h collection, averages of the two weeks as described above will also be used to impute missing UP/UC from the 24h collection.

For the derivation of CRR using UP/UC from the spot urine, the imputation would be as follows: If UP/UC from the spot urine is missing at week 26, then use week 21. If UP/UC from the spot is missing at 52; use 46.

If no serum creatinine value (to determine eGFR) is available at baseline, then it will be imputed using the value at the screening visit. If no serum creatinine value is available at week 26 or week 52 then it will be imputed using the value at week 21 or week 46, respectively.

For secondary endpoints based on proteinuria and eGFR, the same imputation rules will be applied to derive response at weeks 26 and 52.

Definition/derivation of CRR for patients who prematurely stop trial medication

The rules below will be applied to derive CRR/PRR/MRR for the ITT:

Proprietary confidential information © 2020 Boehringer Ingelheim International GmbH or one or more of its affiliated companies

- (1) If the reason for discontinuation of treatment is ‘Lack of efficacy’ or AE type is ‘Worsening of disease under study’, then CRR will be defined as ‘Non-responder’.
- (2) If the patient used prohibited meds known to impact CRR following discontinuation of study med, then CRR will be defined as ‘Non-responder’.
- (3) If neither #1 or #2 apply and treatment duration ≥ 46 weeks, then use the lab data collected at Visit 16-EOT/Week 52 to derive the endpoints. If there is no lab data at Visit 16-EOT /Week 52, then use the lab data closest to 52 weeks that is within 6 weeks prior to week 52.
- (4) If neither #1 or #2 apply and treatment duration < 46 weeks, then CRR will be defined as ‘Non-responder’.

Note that patients handled with the above rules are included in the ITT population. They would only be included in the PPS if they complete 46 weeks of the treatment regimen.

For patients who took study drug for < 46 weeks, continued to participate in the trial and have urine collections and serum creatinine determinations, their data will be displayed in a listing.

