5. ENDPOINT

5.1 PRIMARY ENDPOINT

The primary endpoint is the proportion of patients with CRR at week 52, where CRR is defined as:

UP<0.5 g/d at week 52

and either

eGFR within normal range at week 52

or

decrease in eGFR<20% from baseline at week 52 if eGFR is below normal range (i.e., below Lower Limit of Normal, where LLN =90 ml/min)

For the assessment of proteinuria for the primary and secondary endpoints, 24h urine collection was performed at baseline, 26 and 52 weeks. Collection was performed in duplicate (2 times 24h collection). The value of proteinuria is the average of the two values. Blinded review of the volumes of the 24h collections and durations of collection raised concern that some collections may have been incomplete. It was decided that the 24h samples should be $\geq 500\text{mL/day}$ and at least 19.5 hours (approximately 80% of 24 hours) to be evaluable. With respect to UP, any collections $< 500\text{mL/day}$ or < 19.5 hours were not evaluated.

Rules for deriving UP from 24h urine collections to determine CRR

Protein excretion rates were transferred to BI in units of mg/dL. The following steps were performed to convert to g/day for deriving CRR.

Protein excretion rate (mg/dL) x 1/100 = Protein excretion rate (mg/ml)

Protein excretion rate (mg/ml) x 24-hour total volume (ml) = UP (mg)

UP (mg) * 1/1000= UP (g/day)

After the interim analysis the team had concerns around how well the thresholds ($\geq 500\text{mL/day}$ and at least 19.5 hours) set for evaluability compensated for incomplete 24h collections. Another method to account for incomplete 24h collections was introduced and CRR was also derived based on the ratio of urine protein/urine creatinine (UP/UC) determined from the 24h collections. As the total amount of creatinine excreted daily in the urine is quite stable, UC is used to stabilize the estimate of proteinuria and is generally accepted as a correction for incomplete collections. With this version of the TSAP, this alternate derivation is incorporated. CRR derived using the UP/UC determination will be analysed and presented using the same methods/format used for CRR derived from UP. There is no change to the eGFR component of the definition; it will be calculated from serum creatinine as defined in the CTP.

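### SAP 6.6.1 counts prohibited medication as non-response only after study drug has been stopped, so the same use on drug can still score as a complete renal response in the primary ITT analysis

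*SAP*

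**What the plan says.** SAP 6.6.1 has two branches.

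- **Patients who stop early.** Four rules stand under the heading "Definition/derivation of CRR for patients who prematurely stop trial medication". Rule 1 fails stops for lack of efficacy or worsening of the study disease. Rule 2 fails the patient "If the patient used prohibited meds known to impact CRR following discontinuation of study med". Rule 3 covers remaining stops with at least 46 weeks of treatment: "then use the lab data collected at Visit 16-EOT/Week 52 to derive the endpoints". Rule 4 fails remaining stops before 46 weeks.
- **Patients who do not stop.** Under "Handling missing data for patients who do not prematurely stop trial medication" there is only imputation of missing urine and creatinine values.

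SAP 5.1 ("The primary endpoint is the proportion of patients with CRR at week 52, where CRR is defined as") defines the endpoint by urine protein and eGFR, with no condition on medication. The ITT set in SAP 6.3 ("This patient set includes all patients from the treated set who have a baseline (or screening) proteinuria", together with an eGFR value) has none either, and SAP 7.4.1 makes it the primary analysis set.

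On-drug use is foreseen. SAP Table 6.2:1 lists code D1, "Prohibited medication use", for most agents through week 52, and code G1 for patients not removed from therapy. Both lead at most to exclusion from the per-protocol set, to be decided at a meeting. Protocol 4.2.2.1 says study medication should be permanently discontinued if a restricted therapy becomes necessary.

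**The concern.** By writing rule 2, the sponsor has judged that normal laboratory values reached with the help of such an agent are not a response to study drug. The rule applies that judgement after the last dose but not before it. A patient taken off drug as the protocol directs is a non-responder if the stop comes before week 46, or if it comes later and use continues. A patient kept on drug against the protocol, taking the same agent, can be a complete responder. For these patients the primary outcome depends on whether and when study drug was stopped, so the deviation is scored more favourably than compliance.

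**Working it through.** **Following the rules for each type of patient (week 52, ITT)**

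| Use of a prohibited agent known to impact CRR | Study drug | Rule that decides | Score |
|---|---|---|---|
| On drug | Stopped before week 46 | 4 (or 1 or 2) | Non-responder |
| On drug, continued afterwards | Stopped at week 46 or later | 2 | Non-responder |
| Only after stopping | Stopped at week 46 or later | 2 | Non-responder |
| On drug, not afterwards | Stopped at week 46 or later, reason outside rule 1 | 3 | Laboratory values |
| On drug | Completed | None of 1 to 4 | Laboratory values |

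The last two rows are the gap. The protocol's rule that non-completers are failures (7.5) does not reach a patient who completes. At week 52, rule 2 decides the outcome only for stops at week 46 or later, because rule 4 already fails earlier ones.

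**The plan's own figure, as background.** Protocol 7.7 gives 82% success for 25/30/38/44% with 40:20:20:40 patients at one-sided 20%. A simulation with assumed candidate-shape parameters (the public text does not show them) gives 83.1%. A pairwise comparison of 240 mg with placebo gives 83.3%. The concern does not rest on this figure.

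**One patient.** 1/40 = 2.5 points and 1/20 = 5 points. One extra placebo responder takes 10/40 = 25% to 11/40 = 27.5%, and the planned 44.0 − 25.0 = 19.0 points becomes 16.5. One extra responder at 240 mg makes it 46.5 − 25.0 = 21.5.

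**Dependence on unknown rates.** Let q be an arm's share of such users, r their CRR rate by laboratory values and p the planned rate, taken as the rate among non-users. The present rule gives an observed rate of (1 − q)p + qr; scoring users as failures gives (1 − q)p. The change in the 240 mg minus placebo difference is therefore r(q_placebo − q_240). The cases below assume r = 1/3 and q linear in dose.

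| Assumed q, placebo to 240 mg | Difference, present rule | Difference, users failed | Approximate power, present → users failed |
|---|---|---|---|
| 5% to 2% | 43.79 − 25.42 = 18.4 | 43.12 − 23.75 = 19.4 | 82.9% → 85.4% |
| 2% to 5% | 43.47 − 25.17 = 18.3 | 41.80 − 24.50 = 17.3 | 82.7% → 80.7% |
| 5% in all arms | 43.47 − 25.42 = 18.05 | 41.80 − 23.75 = 18.05 | 82.1% → 82.6% |

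Power here is Φ(ncp − 0.8416), with ncp = √Σw(logit p − weighted mean)² and w = np(1 − p). This is the best single contrast, without multiplicity adjustment or the 10-point criterion. The ncp values are 1.791 → 1.897, 1.785 → 1.707 and 1.761 → 1.782. At the planned rates ncp is 1.852, or 84.4%, which is 2.4 points above the protocol's 82%. That gap is about as large as the shifts in the table, so the table shows only that the sign depends on which arm has more use.

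**The case against.** **ITT principle.** Scoring patients on laboratory values whatever else they took is a defensible treatment-policy approach. That does not settle the matter here, because rules 1, 2 and 4 already override laboratory values. The objection does show that covering all on-drug use is broader than the late window in which rule 2 now decides week 52.

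**Already handled.** A reader might infer that the plan has no check on these patients. The documents do not support that. SAP Table 6.3:1 schedules a per-protocol analysis of CRR at week 52, and D1 and G1 can remove patients from that set, so it may partly show the effect. SAP 7.4.2 has no visible text, and SAP 7.4.1 points to further specification in Section 9, which is not public. Further handling there cannot be ruled out.

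**Deviation windows.** Protocol Table 4.2.2.1:1 does not permit IV glucocorticoids in weeks 26 to 52, while D1 counts "IV glucocorticoids during Week 40-52". It is tempting to call this an error. D1 defines important deviations, however, and SAP Section 4 says these were revised with expert input, so the narrower window may be a deliberate threshold.

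**Steroids.** Nor do the documents support treating every steroid increase as failure. Protocol 4.2.1 allows an increase for worsening or flare with study drug continued. Amendment 6 deleted the steroid-failure rules and left details to the SAP.

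**Late change.** The SAP was revised after the interim analysis, and Protocol 4.1.5.1 required only some of the trial team to stay blinded. Recoding the primary endpoint now carries its own risk of bias. This stands and shapes the fix.

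**Conclusion.** The gap is real in the visible text: two kinds of patient with on-drug use can be complete responders in the primary analysis, while rule 2 treats use after stopping as failure. Its reach is narrow, because the protocol directs such patients off drug and rule 4 fails every stop before week 46.

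A reader might infer a bias towards BI 655064, or a definite loss of power. Neither follows. The documents give no rates of on-drug use by arm, so size and direction cannot be determined. More such responders on placebo would flatten the dose-response curve; more on active drug would steepen it. The firm figure is 2.5 or 5 observed points per patient, depending on the arm; the modelled benefit would move by a different amount. This is a point to consider, not a threat to the design. It assumes that the sections not visible do not already extend rule 2.

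**What to change.** Reword rule 2 to apply to all ITT patients: post-randomisation use, before the assessment concerned (week 26 or week 52), of a prohibited medication known to impact CRR is non-response, whether or not study drug was stopped.

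- Blinded staff should list the agents, and the window that counts for each endpoint, before final unblinding.
- Report the existing rule alongside as a sensitivity analysis, because the change would follow the interim analysis.
- Use that the protocol permits should not be scored as failure by this rule: azathioprine in weeks 26 to 52 under the protocol's conditions, and steroid increases for flare. Pre-randomisation use under D1 remains an eligibility deviation.
- Reconcile the IV glucocorticoid windows in Protocol Table 4.2.2.1:1 and SAP Table 6.2:1, or state that the difference is intended.

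The change concerns outcome coding only. It uses deviation and concomitant-medication data already collected. The cost is one reworded rule, a short list, a little extra programming and possibly slightly lower response rates.
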